## 10.1.11. Publication Policy

For multicenter trials, the primary publication will be a joint publication developed by the investigator and Pfizer reporting the primary endpoint(s) of the study covering all study sites. The investigator agrees to refer to the primary publication in any subsequent publications. Pfizer will not provide any financial compensation for the investigator's participation in the preparation of the primary congress abstract, poster, presentation, or primary manuscript for the study.

Investigators are free to publish individual center results that they deem to be clinically meaningful after publication of the overall results of the study or 12 months after primary completion date or study completion at all sites, whichever occurs first, subject to the other requirements described in this section.

The investigator will provide Pfizer an opportunity to review any proposed publication or any other type of disclosure of the study results (collectively, "publication") before it is submitted or otherwise disclosed and will submit all publications to Pfizer 30 days before submission. If any patent action is required to protect intellectual property rights, the investigator agrees to delay the disclosure for a period not to exceed an additional 60 days upon request from Pfizer. This allows Pfizer to protect proprietary information and to provide comments, and the investigator will, on request, remove any previously undisclosed confidential information before disclosure, except for any study-intervention or Pfizer-related information necessary for the appropriate scientific presentation or understanding of the study results. For joint publications, should there be disagreement regarding interpretation and/or presentation of specific analysis results, resolution of, and responsibility for, such disagreements will be the collective responsibility of all authors of the publication.

For all publications relating to the study, the investigator and Pfizer will comply with recognized ethical standards concerning publications and authorship, including those established by the International Committee of Medical Journal Editors. The investigator will disclose any relationship with Pfizer and any relevant potential conflicts of interest, including any financial or personal relationship with Pfizer, in any publications. All authors will have access to the relevant statistical tables, figures, and reports (in their original format) required to develop the publication.

## 10.1.12. Sponsor's Medically Qualified Individual

The sponsor will designate a medically qualified individual (MQI), also known as the medical monitor, to advise the investigator on study-related medical questions. The contact information for the study medical monitor is documented in the Study Team Contact List located in the site binder/investigator site file.

Participants are provided with a Pfizer study information card at the time of informed consent which includes contact information for their investigator in case of study-related medical questions. The study information card contains, at a minimum, (a) study number, (b) participant's study identification number, and (c) principal investigator contact information.

## 10.2. Appendix 2: Clinical Laboratory Tests

If appropriate, a pregnancy test will be performed at times defined in the SoA.

 Pregnancy test (β-hCG): Local urine testing will be standard for the protocol unless serum testing is required by local regulation or IRB/EC for participants who are WOCBP.

Unscheduled clinical laboratory measurements may be obtained at any time during the study to assess any perceived safety issues. The investigator must review the laboratory report, document this review, and record any clinically relevant changes occurring during the study in the AE section of the CRF.

# 10.3. Appendix 3: Adverse Events: Definitions and Procedures for Recording, Evaluating, Follow-Up, and Reporting

#### 10.3.1. Definition of AE

#### AE Definition

- An AE is any untoward medical occurrence in a patient or clinical study participant, temporally associated with the use of study intervention, whether or not considered related to the study intervention.
- Note: An AE can therefore be any unfavorable and unintended sign (including an abnormal laboratory finding), symptom, or disease (new or exacerbated) temporally associated with the use of study intervention.

## Events Meeting the AE Definition

- Any abnormal laboratory test results (hematology, clinical chemistry, or urinalysis)
  or other safety assessments (eg, ECG, radiological scans, vital sign measurements),
  including those that worsen from baseline, considered clinically significant in the
  medical and scientific judgment of the investigator. Any abnormal test results that
  meet any of the conditions below must be recorded as an AE:
  - Is associated with accompanying symptoms.
  - Requires additional diagnostic testing or medical/surgical intervention.
  - Leads to a change in study dosing (outside of any protocol-specified dose adjustments) or discontinuation from the study, significant additional concomitant drug treatment, or other therapy.
- Exacerbation of a chronic or intermittent preexisting condition, including an increase in either frequency and/or intensity of the condition.
- New condition detected or diagnosed after study intervention administration, even though it may have been present before the start of the study.
- Signs, symptoms, or the clinical sequelae of a suspected drug-drug interaction.
- Signs, symptoms, or the clinical sequelae of a suspected overdose of either study
  intervention or a concomitant medication. Overdose per se will not be reported as an
  AE or SAE unless it is an intentional overdose taken with possible
  suicidal/self-harming intent. Such overdoses should be reported regardless of
  sequelae.

## Events NOT Meeting the AE Definition

- Any clinically significant abnormal laboratory findings or other abnormal safety
  assessments that are associated with the underlying disease, unless judged by the
  investigator to be more severe than expected for the participant's condition.
- The disease/disorder being studied or expected progression, signs, or symptoms of the disease/disorder being studied, unless more severe than expected for the participant's condition.
- Medical or surgical procedure (eg, endoscopy, appendectomy): the condition that leads to the procedure is the AE.
- Situations in which an untoward medical occurrence did not occur (social and/or convenience admission to a hospital).
- Anticipated day-to-day fluctuations of preexisting disease(s) or condition(s) present or detected at the start of the study that do not worsen.

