#### 1. PROTOCOL SUMMARY

### 1.1. Synopsis

Protocol Title: A Phase 3, Randomized, Observer-Blinded Study to Evaluate the Safety, Tolerability, and Immunogenicity of a Combined Modified RNA Vaccine Candidate Against COVID-19 and Influenza in Healthy Individuals

Brief Title: A Study to Evaluate the Safety, Tolerability, and Immunogenicity of a Combined Modified RNA Vaccine Candidate Against COVID-19 and Influenza

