# 8.4.7. Disease-Related Events and/or Disease-Related Outcomes Not Qualifying as AEs or SAEs

Not applicable.

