#### 8.4.8.1. Lack of Efficacy

The investigator must report signs, symptoms, and/or clinical sequelae resulting from lack of efficacy. Lack of efficacy or failure of expected pharmacological action is reportable to Pfizer Safety only if associated with an SAE.

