- Intercurrent events and missing data: Assay results below the LLOQ will be handled as specified in Section 5.3. Missing data will not be imputed. Assay data after a postbaseline new onset of influenza or SARS-CoV-2 infection will be excluded from the analysis of the related immunogenicity endpoint using the evaluable immunogenicity population.
- Reporting results: The unadjusted GMR and the associated 2-sided 95% CI, along with
 the GMTs and the associated 2-sided 95% CIs for each vaccine group, will be provided.
 The number/percentage of participants with seroconversion/seroresponse and the
 corresponding 95% CIs for each vaccine group, and the difference in percentage of
 participants with seroconversion/seroresponse between the 2 comparison groups and
 associated 2-sided 95% CIs, will be calculated.

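### An unadapted template bullet in Appendix 3, read literally, lets sites leave nonserious influenza or COVID-19 after vaccination out of the primary 4-week AE endpoint

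*Protocol*

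**What the plan says.** Protocol Section 8.4 refers to Appendix 3 for the definitions of AE and SAE, so Appendix 3 is the rule that sites work from. Section 10.3.1 in that appendix holds three statements that bear on this point.

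- The definition: "An AE is any untoward medical occurrence in a patient or clinical study participant, temporally associated with the use of study intervention". The note beneath it says that a disease, new or exacerbated, can be an AE.
- Under *Events Meeting the AE Definition*: "New condition detected or diagnosed after study intervention administration, even though it may have been present before the start of the study".
- Under *Events NOT Meeting the AE Definition*: "The disease/disorder being studied or expected progression, signs, or symptoms of the disease/disorder being studied, unless more severe than expected". The sentence goes on to tie the expected severity to the condition of the participant.

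Section 8.4.7 is reserved for "Disease-Related Events and/or Disease-Related Outcomes Not Qualifying as AEs or SAEs". Its whole content is "Not applicable".

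The title describes the product as a "Combined Modified RNA Vaccine Candidate Against COVID-19 and Influenza in Healthy Individuals". No visible text says what the disease under study is for the purpose of the Appendix 3 bullet.

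The primary safety estimands include the percentage of participants with AEs in the 4 weeks after vaccination (Protocol Section 3; SAP Sections 2.2 and 6.1.1.2.1). Neither document says in visible text whether influenza or COVID-19 illness counts toward that percentage.

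**The concern.** The third statement suits a trial in patients who enter with the disease, where its ordinary course should not fill the AE tables. Here participants enter well, and the diseases the product targets are ones they might newly acquire. Taken at face value, the bullet says that an ordinary case of influenza or COVID-19 after vaccination is not an AE. The other two statements, and the empty Section 8.4.7, say that it is.

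At stake is the completeness of a primary safety count. If one site records a mild COVID-19 illness in week 3 as an AE and another leaves it off the CRF, the any-AE percentage, the relevant system organ class and the preferred term all depend partly on which sentence each site followed. The SAP also needs to know when infections began: "Assay data after a postbaseline new onset of influenza or SARS-CoV-2 infection will be excluded from the analysis". An AE record with an onset date would be one natural source for that.

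**Working it through.** The point rests on wording. No alpha, margin, power or sample size depends on it. The only stated safety figures, in Protocol Table 8, follow 1 − (1 − p)^n and reproduce in all 21 entries (for example n = 3000, p = 0.1%: 95.03% against the stated 95.0%), so that table is not in question.

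**Step 1: apply each passage to one case.** Take a participant who is well at entry and has a mild, outpatient influenza illness between vaccination and Visit 2.

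| Place in protocol | Result for this case |
|---|---|
| 10.3.1, definition and note | AE: a new disease, temporally associated |
| 10.3.1, *Events Meeting the AE Definition* | AE: a new condition diagnosed after administration |
| 10.3.1, *Events NOT Meeting the AE Definition* | Not an AE, if influenza is the disease under study and the illness is no worse than expected |
| 8.4.7 | No exemption declared, so nothing removes AE status |

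Three lines point one way and one points the other. The dissenting line sits in the appendix that Section 8.4 names as the source of the definition. No visible text ranks these passages or says that the bullet does not apply.

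**Step 2: what is captured whichever way a site reads it.** Section 8.4.1 has deaths, pneumonia and hospital admissions recorded for the whole study. The bullet also returns illness of more than expected severity to AE status. What remains exposed is nonserious outpatient illness, and for the primary AE endpoint only that in the first 4 weeks.

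**Step 3: size, on an assumed attack rate.** The documents give none. Assume that 0.5% to 2% of participants have influenza or COVID-19 illness within 4 weeks.

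- Arm C: 4500 × 2/3 = 3000. Cases: 3000 × 0.005 = 15 to 3000 × 0.02 = 60.
- Arm D: 4500 × 1/3 = 1500. Cases: 1500 × 0.005 = 7.5 to 1500 × 0.02 = 30.
- Arms E and F: 3600 × 2/6 = 1200 each. Cases: 6 to 24 each.
- Arms G and H: 3600 × 1/6 = 600 each. Cases: 3 to 12 each.

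A wider range of 0.25% to 3% gives 7.5 to 90 in Arm C and 3.75 to 45 in Arm D. These are upper bounds on the change in the any-AE percentage, because a participant with another AE is counted anyway. Cases that are serious or worse than expected also stay in.

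**Step 4: effect on reporting tier.** SAP Section 5.2.1 makes a preferred term Tier 2 once at least 1% of participants in one arm report it: 30 in Arm C, 15 in Arm D, 12 in Arms E and F, 6 in Arms G and H. The assumed range straddles these thresholds. They apply term by term, and influenza and COVID-19 would normally be coded apart, so the combined rate would be split between them. Site reading could decide whether a term gets a between-arm difference with an interval, but only if the rate for that term is near 1%.

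**The case against.** The strongest reply is that the bullet has nothing to act on. Its closing words measure severity against the condition of the participant, and neighbouring bullets speak of underlying and preexisting disease. Participants here have no influenza or COVID-19 at entry, and Section 5.1 marks disease characteristics as not applicable. A careful site would see template text, read the definition together with the empty Section 8.4.7, and record the illness. That is a reasonable reading, and it is why this is an ambiguity and not an instruction to omit cases. But nothing tells sites to read it so, and a site that follows the bullet as written can point to the protocol.

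It is also fair that the safety objective is descriptive, that randomization is site-based, and that those who assess safety are blinded. A site would be expected to apply its reading about equally to its arms.

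Three stronger readings are tempting, and the documents do not support them.

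- **Biased arm comparison.** A reader might infer one. With blinded assessment within sites, the expected effect is lower recorded rates in both arms. Nothing shows a difference in omission between arms.
- **Conflict with Section 8.4.8.1.** That section says "The investigator must report signs, symptoms, and/or clinical sequelae resulting from lack of efficacy". It does not say that they are reported as AEs, and it limits reports to the sponsor's safety group to cases with an SAE. It can stand beside either reading.
- **Distorted Week 4 titres.** The SAP exclusion does depend on knowing infection onset, but the text on testing for influenza and SARS-CoV-2 exposure is redacted, so it cannot be said that the AE record is what identifies infections. Any shift in geometric mean titre from missed infections would also largely cancel in the ratio if infection rates are similar across arms.

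**Conclusion.** The inconsistency stands, and its reach is limited. One unadapted bullet in Appendix 3, read literally, removes nonserious influenza and COVID-19 from the AE definition, against the definition and inclusion list in the same appendix and against Section 8.4.7. The consequence is a primary 4-week AE count that may be incomplete and may vary by site. On the assumed 0.5% to 2% attack rate, a few tens of participants at most per arm are affected, up to 60 in the largest. The conclusion does not depend on that rate, which only sets the scale. No visible text shows that sites have in fact read the bullet differently, and no hypothesis test or decision rule is affected.

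**What to change.** Delete the bullet, or limit it to conditions already present at entry. Add a sentence to Appendix 3 that influenza and COVID-19 with onset after vaccination are recorded as AEs, with onset date, within the existing AE collection period. Section 10.3.1 would then agree with itself and with Section 8.4.7.

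The cost is a short protocol clarification and a memo to sites. Design, sample size and analysis methods are unchanged. Recorded AE rates may rise slightly. If the clarification comes after some participants have passed Visit 2, the study report should say which of them were followed under the ambiguous text.

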### 10.3.2. Definition of an SAE

An SAE is defined as any untoward medical occurrence that, at any dose, meets one or more of the criteria listed below:

### Results in death

## Is life-threatening

The term "life-threatening" in the definition of "serious" refers to an event in which the participant was at risk of death at the time of the event. It does not refer to an event that hypothetically might have caused death if it were more severe.

## c. Requires inpatient hospitalization or prolongation of existing hospitalization

In general, hospitalization signifies that the participant has been admitted (usually involving at least an overnight stay) at the hospital or emergency ward for observation and/or treatment that would not have been appropriate in the physician's office or outpatient setting. Complications that occur during hospitalization are AEs. If a complication prolongs hospitalization or fulfills any other serious criteria, the event is serious. When in doubt as to whether "hospitalization" occurred or was necessary, the AE should be considered serious.

Hospitalization for elective treatment of a preexisting condition that did not worsen from baseline is not considered an AE.

## d. Results in persistent or significant disability/incapacity

- The term disability means a substantial disruption of a person's ability to conduct normal life functions.
- This definition is not intended to include experiences of relatively minor medical significance, such as uncomplicated headache, nausea, vomiting, diarrhea, influenza, and accidental trauma (eg, sprained ankle), that may interfere with or prevent everyday life functions but do not constitute a substantial disruption.

## e. Is a congenital anomaly/birth defect

## f. Is a suspected transmission via a Pfizer product of an infectious agent, pathogenic or nonpathogenic

The event may be suspected from clinical symptoms or laboratory findings indicating an infection in a participant exposed to a Pfizer product. The terms "suspected transmission" and "transmission" are considered synonymous. These cases are considered unexpected and handled as serious expedited cases by pharmacovigilance personnel. Such cases are also considered for reporting as product defects, if appropriate.

## g. Other situations:

- Medical or scientific judgment should be exercised by the investigator in deciding
  whether SAE reporting is appropriate in other situations, such as significant medical
  events that may jeopardize the participant or may require medical or surgical
  intervention to prevent one of the other outcomes listed in the above definition.
  These events should usually be considered serious.
- Examples of such events include invasive or malignant cancers, intensive treatment in an emergency room or at home for allergic bronchospasm, blood dyscrasias or convulsions that do not result in hospitalization, or development of drug dependency or drug abuse.

# 10.3.3. Recording/Reporting and Follow-Up of AEs and/or SAEs During the Active Collection Period

## AE and SAE Recording/Reporting

The table below summarizes the requirements for recording AEs on the CRF and for reporting SAEs using the Vaccine SAE Report Form or via PSSA to Pfizer Safety throughout the active collection period. These requirements are delineated for 3 types of events: (1) SAEs; (2) nonserious AEs; and (3) exposure to the study intervention under study during pregnancy or breastfeeding, and occupational exposure.

It should be noted that the Vaccine SAE Report Form/PSSA for reporting of SAE information is not the same as the AE page of the CRF. When the same data are collected, the forms must be completed in a consistent manner. AEs should be recorded using concise medical terminology and the same AE term should be used on both the CRF and the Vaccine SAE Report Form/PSSA for reporting of SAE information.

Safety Event	Recorded on the CRF	Reported on the Vaccine SAE Report Form/PSSA to Pfizer Safety Within 24 Hours of Awareness
SAE	All	A11
Nonserious AE	All	None
Exposure to the study intervention under study during pregnancy or breastfeeding	All AEs or SAEs associated with EDP or EDB	All instances of EDP are reported (whether or not there is an associated SAE)*
	Note: Instances of EDP or EDB not associated with an AE or SAE are not captured in the CRF	All instances of EDB are reported (whether or not there is an associated SAE)**
Environmental or occupational exposure to the product under study to a nonparticipant (not involving EDP or EDB)	None. Exposure to a study nonparticipant is not collected on the CRF	The exposure (whether or not there is an associated AE or SAE) must be reported***

EDP (with or without an associated SAE) is reported to Pfizer Safety using the Vaccine SAE Report Form and EDP Supplemental Form or via PSSA.

When an AE or SAE occurs, it is the responsibility of the investigator to review all
documentation (eg, hospital progress notes, laboratory reports, and diagnostic
reports) related to the event.

\*\* EDB is reported to Pfizer Safety using the Vaccine SAE Report Form or via PSSA, which would also include details of any SAE that might be associated with the EDB.

\*\*\* Environmental or occupational exposure: AEs or SAEs associated with occupational exposure are reported to Pfizer Safety using the Vaccine SAE Report Form or via PSSA.

- The investigator will then record all relevant AE or SAE information in the CRF.
- It is not acceptable for the investigator to send photocopies of the participant's medical records to Pfizer Safety in lieu of completion of the Vaccine SAE Report Form/AE or SAE CRF page.
- There may be instances when copies of medical records for certain cases are requested by Pfizer Safety. In this case, all participant identifiers, with the exception of the participant number, will be redacted on the copies of the medical records before submission to Pfizer Safety. Refer to Section 10.1.9 for actions that must be taken when medical records are sent to the sponsor or sponsor designee.
- The investigator will attempt to establish a diagnosis of the event based on signs, symptoms, and/or other clinical information. Whenever possible, the diagnosis (not the individual signs/symptoms) will be documented as the AE or SAE.

## Assessment of Intensity

The investigator will make an assessment of intensity for each AE and SAE reported during the study and assign it to 1 of the following categories:

GRADE	If required on the AE page of the CRF, the investigator will use the adjectives MILD, MODERATE, SEVERE, or LIFE-THREATENING to describe the maximum intensity of the AE. For purposes of consistency, these intensity grades are defined as follows:		
1	MILD	Does not interfere with participant's usual function.	
2	MODERATE	Interferes to some extent with participant's usual function.	
3	SEVERE	Interferes significantly with participant's usual function.	
4	LIFE-THREATENING	Life-threatening consequences; urgent intervention indicated.	

An event is defined as "serious" when it meets at least 1 of the predefined outcomes as described in the definition of an SAE, NOT when it is rated as severe.

